7.2 Imputations

For cases when baseline ALT/Pro-C3 values are missing, the (log transformed) baseline values will be imputed by the average value of (log-transformed) baseline for all non-missing. For post-baseline missing ALT/Pro-C3 values, a distinction in the imputation will be made between non-monotone and monotone missing data. Monotone missing data are defined on a subject level as missing data that constitutes the end of subject follow-up, while non-monotone missing data means that observations exist after the time point with the missing data. The steps of the imputation algorithm are described in [Table 1](#).

There are some preparations of the datasets needed prior to starting with the imputations. Each subject must have a record for all measurements indicated by the protocol; for visits where a subject did not attend or did not get a measurement, a record with the value “.” must be included into the dataset. Furthermore, indicators for last visit on treatment, and whether the subject had treatment through the whole intended treatment period of 12 weeks must also be included.

Table 1 Missing data imputation algorithm, including analysis

Step		Description
1	Impute missing baseline	For all missing (log-transformed) baseline values, impute with the average of all non-missing (log-transformed) baseline values in the FAS population.
2	Impute non-monotone missing data	Impute all non-monotone missing data using the Markov Chain Monte Carlo (MCMC) method assuming missing data are CCI [REDACTED]. This is performed using PROC MI in SAS, stratified by CCI [REDACTED], with the

		
CCI and CCI options in the MCMC statement. CCI will be generated using the seed 35273, CCI. The imputation model will include CCI assessments CCI.

3	Impute monotone missing data	
For each of the CCI imputed datasets, impute all monotone missing ALT (Pro-C3) data CCI.
 
The CCI model imputation with a CCI will be performed with the seed 99463734. The statement is CCI.
 
Subjects who had missing data CCI.
 
The CCI imputation will be conducted following a process CCI. This will involve CCI.
 
The process will utilize the seed 101010. Please note that the term CCI will need to be adjusted to reflect CCI in the dataset.

4	Analyse	Fit the pre-specified LME model with variance-covariance matrix structure set to SP(POW)(week) to each imputed

		
dataset, all without any missing data, using CCI [REDACTED] If not all CCI [REDACTED] models converge, follow the approach given in section 4.2.1.4.
 
Store the CCI [REDACTED] resulting least square mean estimates for each treatment group and the difference between treatment groups, and the corresponding standard errors for each model.

5	Pool model estimates	
Pool results using CCI [REDACTED] in SAS by visit to provide the final least square mean estimates and 95% CIs in log scale, together with p-value for the two-sided test for difference between treatment groups. Estimates will be transformed back to the original scale (to describe ratio to baseline in terms of geometric means and, furthermore, to describe percent change versus baseline within group and percent change versus placebo in ratio to baseline for the 5mg group compared to placebo). CCI [REDACTED]

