### Statistical Methods

The primary pharmacodynamic endpoint of this study is change from baseline to Week 12 in alanine aminotransferase (ALT), and it will be assessed through a treatment policy estimand. This approach will assess the effect of the treatment policy of AZD4831 (mitiperstat) and placebo regardless of discontinuation of study medication. The main analysis will be using a mixed effects linear model with participant as random effect, treatment, visit, and treatment-by-visit interaction as fixed effects, and baseline as covariate, including all participants in the full analysis set (FAS). Data will be log-transformed before analyses, and results will be back-transformed to describe relative change versus placebo in value at end of treatment relative to baseline.

The null hypothesis of no decrease in ALT comparing AZD4831 (mitiperstat) to placebo will be tested versus the alternative hypothesis of a decrease in ALT in favor of AZD4831 (mitiperstat) to placebo using a one-sided test at 5% significance level.

The secondary endpoint Pro-C3 will be analyzed in the same way as ALT.

The study has been powered to have at least 80% power to detect a 25% decrease in ALT level at end of treatment relative to baseline for AZD4831 (mitiperstat) treated versus placebo treated in a one-sided test at 5% significance level, based on the FAS population. ALT measurements will be log-transformed before analysis. Under the assumption of a standard deviation of 0.50 for change from baseline in log-transformed ALT, and allowing for 10% missing data, 45 participants per arm would render the desired power.

[figure not shown]
Safety analyses will be performed using the safety analysis set, which includes all participants who receive at least 1 dose of randomized AZD4831 (mitiperstat) or placebo. Safety data will be presented using descriptive statistics unless otherwise specified and will not be formally tested.

No multiplicity adjustment for alpha is planned.

All personnel involved with the conduct of the study will remain blinded until database lock at 12 weeks and protocol violations have been identified and documented. Analyses will be performed by AstraZeneca or its representatives.

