## **9.2        Sample Size Determination**

The study has been powered to have at least 80% power to detect a 25% decrease in ALT level at end of treatment relative to baseline for AZD4831 (mitiperstat) treated versus placebo treated in a one-sided test at 5% significance level, based on the FAS population. Alanine aminotransferase measurements will be log-transformed before analysis. Under the assumption of a standard deviation of 0.50 for change from baseline in log-transformed ALT,

and allowing for 10% missing data, 45 participants per arm would render the desired power.

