#### **9.4.1 General Considerations**

All personnel involved with the analysis of the study will remain blinded until database lock and protocol violations have been identified and documented. Analyses will be performed by AstraZeneca or its representatives.

Nominal significance will be 5% and all tests will be one-sided. All confidence intervals will be 2-sided and 95%.

No multiplicity adjustment for alpha is planned.

For analyses both on the FAS and on the SAS, baseline is defined as the last non-missing value prior to first dose including unscheduled assessments that occurs prior to first dose.

All summary statistics will be presented in total, divided by fibrosis stage, and divided by T2DM status.

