## 9.4.2 Pharmacodynamics

### 9.4.2.1 Primary Endpoint

The primary pharmacodynamic endpoint for this study is change from baseline to Week 12 in log-transformed ALT.

The null hypothesis of no decrease in ALT comparing AZD4831 (mitiperstat) to placebo will be tested versus the alternative hypothesis of a decrease in ALT in favor of AZD4831 (mitiperstat) to placebo using a one-sided test at 5% significance level, assessed through a treatment policy estimand. The endpoint will be analyzed in a mixed effects linear model with participant as random effect, treatment, visit and treatment-by-visit interaction as fixed effects, and baseline as covariate. Data will be log-transformed before analyses, and results will be back-transformed to describe relative change versus placebo in value at end of treatment relative to baseline. Furthermore, data will also be analyzed as individual percental change, that is  $(\text{value at time } t - \text{value at baseline})/(\text{value at baseline})100\%$ , in a similar mixed effects model but without log transformation of data.

- **Treatment:** Treatment with 5 mg AZD4831 (mitiperstat) compared to placebo, administered in addition to optimal background therapy for co-morbidities
- **Population:** FAS
- **Endpoint:** Change from baseline in log-transformed ALT
- **Intercurrent events:** Intercurrent events will be ignored (treatment policy strategy) and potential missing data imputed
- **Population-level summary:** Relative change versus placebo in value at end of treatment relative to baseline

Any missing baseline ALT values will be imputed based on existing baseline values of FAS participants using PROC MI MCMC, disregarding the treatment group. For postbaseline missing ALT values, a distinction in the imputation will be made between non-monotone and monotone missing data. Monotone missing data are defined as missing data that constitute the end participant follow-up, while non-monotone missing data means that there are observations made after the missing time point. Any non-monotone missing data will be replaced using PROC MI MCMC while monotone missing data will use PROC MI regression. The imputation model will include timepoint, baseline value, and treatment group. More details will be described in the SAP.

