#### **9.4.2.2 Secondary Endpoint**

For Pro-C3 the null hypothesis of no decrease comparing AZD4831 (mitiperstat) to placebo will be tested versus the alternative hypothesis of a decrease in favor of AZD4831 (mitiperstat) to placebo in the same way as for ALT. Missing observations will be imputed using the same method as for missing ALT observations.

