1.3 Number of subjects

About 300 subjects are expected to be enrolled to achieve approximately 90 eligible subjects. Subjects will be randomly assigned at a 1:1 ratio to one of the 2 treatment groups listed below:

- AZD4831 5 mg
- Placebo matching dose

The sample size is driven by the objective to assess the efficacy of AZD4831 of lowering alanine aminotransferase (ALT). Accounting for missing data, the randomization scheme described above aims to ensure that there are at least 40 subjects exposed to AZD4831 for 12 weeks, and at least 40 subjects treated with matching placebo for 12 weeks, with evaluable observations of ALT both at baseline and at end of treatment. Under the assumption of a standard deviation of 0.50 for change from baseline in log-transformed ALT, 40 participants per arm would render 80% power to detect a 25% decrease in ALT levels at end of treatment relative to baseline for AZD4831 treated versus placebo treated on a one-sided test with an alpha of 5%. Missing observations will be imputed, but to account for a potential loss in the ability to capture treatment effect when including imputed data, the aim is to randomize 45 participants per arm.

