2 CHANGES TO PROTOCOL PLANNED ANALYSES

Full analysis set have been changed to include patients who are randomized and have been given at least one dose.

Analysis on explorative endpoint *Oxidative damage biomarkers* are not included in CSR.

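### SAP 7.2 step 5 asks for a two-sided p-value for ALT and Pro-C3, although the protocol plans one-sided 5% tests and SAP Section 2 declares no change

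*SAP*

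**What the plan says.** SAP 7.2 (Imputations) covers ALT, the primary endpoint, and Pro-C3, the pharmacodynamic secondary endpoint. Step 5 of its algorithm pools the model results by visit and reports least-squares means and 95% CIs on the log scale, "together with p-value for the two-sided test for difference between treatment groups". Its visible text gives no significance level and no conversion to a one-sided value.

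The other passages on sidedness are:

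- Protocol 9.4.1: "Nominal significance will be 5% and all tests will be one-sided". The same section sets all confidence intervals as two-sided 95%.
- Protocol 9.4.2.1, for ALT: "using a one-sided test at 5% significance level, assessed through a treatment policy estimand". The synopsis has the same test: "decrease in ALT in favor of AZD4831 (mitiperstat) to placebo using a one-sided test at 5% significance level".
- Protocol 9.2, the power statement: "versus placebo treated in a one-sided test at 5% significance level, based on the FAS population".
- Protocol 9.4.2.2, for Pro-C3: "alternative hypothesis of a decrease in favor of AZD4831 (mitiperstat) to placebo in the same way as for ALT".
- SAP 1.3, the ALT sample size: "versus placebo treated on a one-sided test with an alpha of 5"%.

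SAP Section 2 lists two departures from the protocol. One concerns the analysis set: "Full analysis set have been changed to include patients who are randomized and have been given at least one dose". The other leaves one exploratory endpoint out of the CSR. Neither concerns sidedness, and the SAP amendment history records no change to it.

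**The concern.** Step 5 is the instruction a programmer would follow to produce the p-value for the primary comparison. As written, it delivers the p-value of a different test from the one in the protocol. For ALT the SAP also disagrees with itself, because its own sample-size section is one-sided.

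The risk is that the printed number is taken for the result of the planned test. The only significance level in the visible text is 5%, so a reader may compare the printed value with 0.05. A result that meets the planned test could then be reported as missing it, and an increase in ALT could carry a p-value below 0.05. If the choice is settled only after unblinding, it can look data-driven.

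**Working it through.** **Inputs.** A 25% decrease gives a log effect of |ln 0.75| = 0.2877 (Protocol 9.2). The SD of change in log ALT is 0.50 (Protocol 9.2, SAP 1.3). There are 40 evaluable per arm (SAP 1.3), or 45 randomized with 10% missing (Protocol 9.2), allocated 1:1. Alpha is 5% one-sided. The check uses a simple two-sample comparison.

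**1. The plan's own figure.** n per arm = 2 × 0.50² × (1.645 + 0.842)² / 0.2877² = 37.4, so 38. With 10% missing, 38/0.9 = 42.2, so 43. The stated 40 and 45 are slightly generous. At 40 per arm:

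- SE = 0.50 × √(2/40) = 0.1118
- noncentrality = 0.2877/0.1118 = 2.573, with df = 78
- one-sided 5% power = 81.7% (t) or 82.3% (normal)

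This satisfies the protocol's aim of at least 80%. A two-sided 5% test does not reproduce the plan: it would need 48 evaluable and 54 randomized per arm (normal approximation). The sample size was therefore built on the one-sided test.

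**2. Critical values at 40 per arm.**

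- One-sided 5%: t = 1.6646, reduction = 1 − exp(−1.6646 × 0.1118) = 17.0%
- Two-sided 5%: t = 1.9908, reduction = 1 − exp(−1.9908 × 0.1118) = 20.0%

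An observed reduction between about 17% and 20% meets the planned test, yet step 5 would print a p-value between 0.05 and 0.10.

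**3. Examples.**

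| Observed ALT ratio, active/placebo | t | Planned one-sided p | p printed by step 5 |
|---|---|---|---|
| 0.830 (17.0% lower) | −1.665 | 0.050 | 0.100 |
| 0.815 (18.5% lower) | ln 0.815 / 0.1118 = −1.830 | 0.036 | 0.071 |
| 1.25 (25% higher) | ln 1.25 / 0.1118 = +1.996 | 0.975 | 0.049 |

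**4. Power if the printed value were judged at 0.05.** At 40 per arm, power for a 25% decrease would be 71.9% (t) or 73.0% (normal), against 81.7% or 82.3% as planned. No visible text prescribes that reading.

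**The case against.** The strongest case on the other side has four parts.

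- **Unseen text.** SAP 4.2.1 to 4.2.3, which hold the primary and secondary analyses, are not visible, and the end of step 5 is blacked out. A rule linking the two-sided output to the one-sided test may stand there. This limit stands. It would reduce the remedy to a cross-reference.
- **No decision rule in step 5.** It is the pooling step of an appendix and sets no alpha. The one-sided p-value follows exactly from the two-sided value and the sign of the difference printed beside it. That is true, and it is why no power is lost by the wording alone. An increase in ALT would also be visible from the estimate.
- **Section 2 is not a complete list.** Protocol 9.4.2.1 imputes missing baseline ALT by PROC MI MCMC, SAP 7.2 uses the mean of the observed baselines, and Section 2 does not mention this. The SAP also serves three regional protocols, of which one is at hand. So silence in Section 2 is weaker evidence about intent. It still leaves the one-sided test as the only one planned in the documents available.
- **Agreement with the CI.** In the 18.5% example the two-sided 95% CI is exp(−0.2046 ± 1.9908 × 0.1118), or 0.65 to 1.02. It includes 1, and so fits p = 0.071 better than p = 0.036. But Protocol 9.4.1 deliberately pairs one-sided 5% tests with two-sided 95% intervals. The interval convention does not change the test.

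**Conclusion.** The point holds. On the visible current text, step 5 specifies a p-value other than that of the planned test for both ALT and Pro-C3, without a declared change.

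The effect is limited to the reported p-value and how it is read. Observed ALT reductions of about 17% to 20% are where the planned test and a two-sided reading at 0.05 would disagree. The sample size, the planned power of about 82%, the estimate and the CI are not in question, and the fall to 72-73% is conditional on that reading.

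The figures assume the plan's SD of 0.50 and 40 evaluable per arm. They are illustrative for the planned baseline-adjusted mixed model with pooled imputations. The doubling of the p-value when the effect favours active does not depend on them. Confidence is medium because SAP 4.2.1 to 4.2.3 cannot be read. This should be fixed before database lock.

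**What to change.** In SAP 7.2 step 5, for ALT and Pro-C3, state that the p-value for the Week 12 contrast is the pooled one-sided value for the alternative that the active-to-placebo ratio is below 1, tested at 5%. It equals half the two-sided p-value if the pooled log difference is below 0, and 1 minus half of it otherwise. If SAP 4.2.1 to 4.2.3 already say this, a cross-reference is enough. Keep the two-sided 95% CI, and note that it can include 1 when the one-sided test is met.

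If a two-sided 5% test is really intended, list the change in SAP Section 2 and restate the power as about 72-73% at 40 evaluable per arm.

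The cost is one sentence or cross-reference and one output column. The main fix has no operational cost and does not affect the sample size.
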